**Alcohol Use in Youth.** Underage drinking continues to be a significant public health concern in the U.S. and is a priority area for research within NIAAA. Recent data indicate that among youth ages 12-20, about 23% report past month use and nearly 14% report at least one binge episode (5+ drinks) within that same time frame. Results from national epidemiologic studies suggest that use escalates in later adolescence (ages 17-20). In particular, there is a substantial increase in use midway through this stage of development: rates of past 30-day use, 1 or more binge episodes, and heavy use (5+ binge episodes) are 22.7%, 13.1%, and 2.7% among 16-17-year olds. Among 18-20-year olds, these rates jump to 43.8%, 29.1%, and 8.5%, respectively. Among the indicators of riskiest use, binge use more than doubles and heavy drinking more than triples in this age group. This is concerning as alcohol use, particularly risky use, has myriad consequences for adolescents, the people around them, and society as a whole. Individual-level consequences are physical, emotional, and social in nature including death from injuries, engagement in risky sexual behavior, increased risk of sexual and physical assault, academic failure, and changes in brain functioning, which may last into young adulthood. On a societal level, costs of underage drinking were recently estimated at \$24.3 billion.

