KB will refine and complete the digital programming of PN in consultation with the research team. Investigators have developed goals and specific instructional/behavioral objectives and content for the PN in Phase I. During Phase II, KB will iteratively share content with all members of the team who will review and provide feedback for any remaining revisions. We used a combination of emails, telecommunications, Zoom teleconferencing, and in-person meetings in Phase I (meeting weekly and more often as needed). We will utilize this same approach in Phase II. This process will continue until all necessary improvements are made. Following completion of the digital programming for the remaining modules, we will conduct a usability study that mirrors the approach we used in Phase 1. The functionality of the PN program will be tested by KB on a small group of parents (~n = 5-7). Edits will be made based on these findings and then tested again on another small group of parents (~n = 5-7). Based on our experience on the development time in Phase I, we anticipate this process to be completed in 6 months.

**Limitations and Alternative Methods for Objective 1.** Face-to-face delivery and/or a longer curriculum may be more effective in reducing substance use. Future research should compare modalities, but the current design facilitates delivery with minimal training and increased consistency, maximizing usability with varied groups. A native mobile app could be produced but it is more expensive and can take longer to produce for multiple device operating systems, is more challenging to update, and its use cannot be as easily monitored as a web app.

**Milestones/Deliverables for Objective 1.** The benchmark for Objective 1 is when all of the above steps are accomplished and PN is revised to specifications and fully operational with a high degree of usability as expressed in SUS scores above the 68 standard.

**Objective 2: Conduct a randomized clinical trial to evaluate outcomes of the PN curriculum. Randomized Trial Design.** The design is a two-arm RCT (PN vs. active control) with 3 waves of data collection: pre-intervention baseline, short-term follow-up (1-month), and longer-term follow-up (6-month). The study will enroll a nationally representative sample of 400 parent-student dyads through GfK Custom Research (formerly known as Knowledge Networks). Youth will complete assessments of all the variables in

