**Table 1. Randomized Control Trial Study Design**

Condition	N	Target	T 1	Intervention	T 2 – 1 mo	T 3 – 6 mo
Active Control	200	Teens	O pre		O post	O post
		Parents		X SAMHSA	O post	
Treatment	200	Teens	O pre		O post	O post
		Parents		X PN	O post	

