As noted above, teens who complete their consent will be routed to an online survey. After the baseline assessment, parents will be randomized equally to 1 of 2 groups. Parents in the treatment condition will receive a link to KB’s secure server to access PN and complete a brief question set assessing their parent communication style. Parents in the control condition will receive a link to that server to access publicly available SAMHSA alcohol prevention materials for parents. Both conditions take the same length of time to navigate. Parents in both conditions will be instructed to access the materials and discuss the information with their teens during the next month. Thus, the proposed research will have a strong active control condition for which to examine differences in effects increasing the rigor of the study. The link to the website will contain instructions on how to register and use the site. Parents who do not register with the website will receive reminders every 5 days for three weeks; after three weeks, study staff will contact parents by telephone and encourage them to register. RP staff will provide technical assistance if parents have problems using the website. In our previous studies, we have had parental compliance rates with web surveys, parenting materials

from the Parent Handbook, parent-ratings of the Parent Handbook and so on, that have reliably exceeded 88%. We anticipate no problems regarding use of the PN in the proposed research.

Teen participants in both the treatment and control groups will receive a follow-up survey (~15 minutes to complete) at 1 and 6 months post-baseline, which will allow us to examine any changes in the proposed mediator variables. Parents randomized to the PN condition will complete a brief question set at the beginning of the PN intervention that assesses parenting communication style and allows for personalization. Parents also receive an immediate posttest to measure fidelity and reactions to PN. Baseline, 1- and 6-month follow-up surveys will each take approximately 25-30 minutes to complete.

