**Randomization.** GfK starts with estimates for survey completion rate, incidence (confirmation of teen’s age and consent), and the number of subgroups. These estimates are used to determine the estimated number of eligible parents who have children of study age. GfK then selects the sample of parents from their panels. Parents are then screened for eligibility and consented. Parents that provide consent are assigned numbers based on a random number table sequence and then randomly assigned to one of the study arms.

**Data Collection and Measurement.** As noted above, self-report surveys programmed and facilitated by GfK will be completed online, at up to 3 timepoints: baseline and 1- and 6-months post intervention (Table 2). In addition, program analytics will be examined to help ensure fidelity to the intervention, and to be included as covariates in all analyses.

**Self-Report.** Table 2 describes the self-report measures to be assessed, consistent with our conceptual model depicted in Figure 1, including primary, secondary, and tertiary outcomes. As indicated above, both teens and parents will complete online surveys through GfK. This self-report methodology is consistent with major national epidemiological surveys of teen substance use, as well as [name]’s prior work in this area, and is demonstrated to be valid. Participants will be made aware of the importance of the data, the confidential nature of their responses, and that the research team will follow appropriate procedures to secure their privacy.

PN Program Analytics. Program analytics (i.e., log data) to be collected include total time spent accessing PN, time spent on each module and activities within modules, and number of activities and modules completed. These data will be captured through HTML5 programming and downloaded into Excel. From this data, we will be able to examine the depth of parents’ immersion in the program and distinguish between users who quickly moved through the program versus those with a deeper level of engagement as well as assess accuracy and use them to assess effects of program exposure (i.e., dose).

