**Traditional SEM Analyses.** Many of our analyses will use structural equation modeling (SEM). A useful computer program for analyzing complex SEM is Mplus. It offers bootstrapping, robust standard errors, and numerical strategies to deal with mixtures of categorical and continuous endogenous variables. The models tested will generally be statistically over-identified. We will evaluate model fit using both global indices (chi square, the Bollen-Stine bootstrapped chi square, GFI, CFI, standardized RMR, RMSEA, and p-value for the test of close fit) and focused indices of fit diagnostic of specific points of ill fit (standardized residuals for predicted minus observed variances and covariances, modification indices, the presence of offending estimates, etc.). We will compare results of traditional modeling (maximum likelihood) with those from robust standard errors and bootstrapping. We will have increased confidence in coefficients in results across analytic methods. In the face of poor fit, we will examine diagnostics for revising the model that, first and foremost, are conceptually meaningful. Analytic strategies for interaction effects in complex SEM models are somewhat controversial. Mplus offers a quasi-maximum likelihood method that has desirable properties when data are multivariately normally distributed. Marsh et al. suggest a simple strategy for non-normal data, but which should be supplemented with limited simulation analysis to ensure one is not led astray by relaxed model constraints. [name] is skilled at the analysis of interactions in structural equation models and has co-authored several books on the topic. The strategies in Mplus and suggested by Marsh et al. will be pursued as well as limited information estimation approaches using traditional regression models.

[figure not shown]
**Randomization Bias.** We will assess differences at baseline between the groups (PN vs. controls) on major demographic and background variables (e.g., sex, age, education), and if necessary, add these as covariates to the analyses. In our past studies, we have not found significant differences between the groups on these variables when our sample sizes are at the numbers we have proposed (>75 per cell).

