#### *Intervention Materials and Follow-Up Surveys:*

At the 1-month follow-up to the baseline survey teens in both treatment and control conditions which will be surveyed to allow us to examine any changes in proposed mediator variables. After the baseline, dyads will be randomized to the treatment and active control conditions. Parent respondents will receive either PN or the active control (SAMHSA website) link. Parents in both conditions will be instructed to read the materials and discuss the information with their teens during the next month. Both conditions will take the same length of time to navigate, and identical fidelity questions and prompts will be used. Instructions for how to register and use the site will be provided on the home page. Parents who do not register with the website will receive reminders every 5 days for three weeks; after three weeks, study staff will contact parents by telephone and encourage them to register. Implementation of technology interventions can be challenging due to participants forgetting, fatiguing, or believing they have learned all they need. The GfK staff will send periodic reminders to parents to use the website; RP staff will be available to provide technical assistance if parents have problems using the website. In our previous studies, we have had parental compliance rates with e-surveys, hard-copy Parent Handbook, parent-ratings of the Parent Handbook and so on that have reliably exceeded 88%. We anticipate no problems regarding use of the web-PN.

Following the intervention dissemination, teens and parents will be asked to complete an immediate posttest survey (1-month) and teens will complete a second posttest at 6-months following the same procedures as detailed above.

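### Allocation is described without blocks or strata and with two different timings, so baseline drinkers can fall unevenly between arms and no adjustment for baseline drinking is prespecified

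*Combined protocol and SAP*

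**What the plan says.** The method is described once, in the Randomization paragraph of Approach, Objective 2: consenting parents are "assigned numbers based on a random number table sequence and then randomly assigned to one of the study arms". No section names blocks, strata, minimization or a list of fixed size, and none calls the method simple or unrestricted.

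The timing differs between sections. That paragraph moves from parent consent to assignment without mentioning the teen survey. Participant Recruitment and Procedures says "After the baseline assessment, parents will be randomized equally to 1 of 2 groups". Protection of Human Subjects (Intervention Materials and Follow-Up Surveys) says "After the baseline, dyads will be randomized to the treatment and active control conditions".

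On size, "The study will enroll a nationally representative sample of 400 parent-student dyads", and Table 1 shows 200 per arm. Alcohol use is not an entry requirement. For the study ages, the Significance section reports "rates of past 30-day use, 1 or more binge episodes, and heavy use (5+ binge episodes) are 22.7%, 13.1%, and 2.7% among 16-17-year olds". Sources of Material confirms that alcohol use and demographics are asked at baseline.

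For chance imbalance, the Randomization Bias paragraph plans a baseline check on demographic and background variables (sex, age and education are the examples), with covariates added if needed. It adds: "In our past studies, we have not found significant differences between the groups on these variables". The Aim 1 analysis is a 2 x 3 group-by-time MANCOVA with baseline as one of the three time levels. The covariates named there are sex, sexual orientation and gender identity.

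**The concern.** In a universal sample most teens will report little or no drinking at baseline, and baseline drinking is likely to be a strong predictor of the alcohol outcomes. Without restriction on that factor, its balance is left to chance. The plan's reassurance from past studies concerns demographic and background variables and says nothing about drinking.

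An unlucky draw would then enter the Aim 1 contrast. In a change-type comparison, the arm that starts with heavier drinking tends to fall further through regression to the mean. Deciding on a covariate only after seeing the imbalance makes the primary analysis data-dependent.

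The timing conflict matters in its own right. It decides whether baseline answers exist when the arm is drawn, and which dyads belong to the intent-to-treat set, which the plan defines as everyone randomized.

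**Working it through.** **Inputs.** N = 400, 200 per arm (Table 1). Past-30-day use 22.7%, binge 13.1%, heavy use 2.7% (Significance). Effect of 5-10% of outcome variance with power above 0.80 (Statistical Design and Power). Assumed, because the plan gives no figure: two-sided alpha 0.05; baseline/follow-up correlation r = 0.4-0.7; national rates apply to this sample.

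**1. The plan's power figure.** For 5% of variance, f² = 0.05/0.95 = 0.0526 and d = 2√0.0526 = 0.459. With 200 per arm, power is 0.996. At 140 per arm (280 retained at 6 months) it is 0.970. The stated bound of 0.80 holds.

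**2. Arm sizes, if draws are independent 1:1.** With Binomial(400, 0.5), P(exactly 200/200) = 4.0%, P(an arm off by 10 or more) = 34%, and the 95% range is 180 to 220. Relative efficiency at 180/220 is 4 × 180 × 220/400² = 0.99. Power moves from 0.9957 to 0.9954, or from 0.800 to 0.796 for an effect with exactly 80% power. This is immaterial.

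**3. Balance of drinkers.**
- Expected counts: 400 × 0.227 ≈ 91 past-month drinkers, 400 × 0.131 ≈ 52 bingers, 400 × 0.027 ≈ 11 heavy users.
- SE of the arm difference in drinker share: √(0.227 × 0.773 × 2/200) = 0.0419, or 4.2 points; 95% limits ±8.2 points.
- P(5 points or more): 0.05/0.0419 = 1.19 SE, two-sided 23%. P(10 points or more) = 1.7%.
- With arms forced to 200/200 (hypergeometric: 400 teens, 91 drinkers, 200 drawn), P(5 points or more) is again 23%. The simulated 95th percentile of the difference is 8.5 points, against 8.3 under independent draws. Fixing arm sizes does not balance drinkers.
- Within one sex (200 teens, 100 per arm, same rate assumed): SE = √(0.227 × 0.773 × 2/100) = 5.9 points, 95% limits ±11.6.

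**4. Effect on the estimate.** A 1.96-SE imbalance in a standardized baseline score is 1.96 × √(2/200) = 0.196 SD.

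| Comparison | Shift | r = 0.4 | r = 0.7 |
|---|---|---|---|
| Follow-up, unadjusted | r × 0.196 | 0.08 SD | 0.14 SD |
| Change from baseline (opposite sign) | (1 − r) × 0.196 | 0.12 SD | 0.06 SD |
| Follow-up, adjusted for baseline | – | about 0 | about 0 |

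Against d = 0.459, the change-contrast shift is 0.059/0.459 = 13% to 0.118/0.459 = 26% of the smallest effect the plan powers for.

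**5. After stratifying (20,000 simulated allocations, blocks of 4, 91 drinkers).** With drinking-by-sex strata, drinkers differ by at most 3 (1.5 points) and arm totals by at most 6. By counting: each stratum can be off by 2, and because 91 is odd one of the two drinker strata is odd and can be off by only 1, so 2 + 1 = 3.

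**6. What stratifying does not reach.** If the 91 drinkers split 46/45, the chance of a 60/40 or worse split of 52 bingers falls from 13% to 2%. The chance of an 8-3 or worse split of 11 heavy users falls only from 23% to 20%.

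**The case against.** The strongest reply is that this is a gap in description and that analysis can deal with the consequence. Much of that stands.

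- A reader might infer coin-flip randomization that will miss 200/200. The documents do not say so. A randomly ordered list cut in half fits the wording equally well and gives exactly 200/200. The 4% and 34% figures apply only under independent draws. The drinker figures apply under either reading.
- Baseline is already in the Aim 1 model, as a time level, and the covariate examples are open-ended. But a time level is not a covariate. A group-by-time contrast keeps the regression-to-the-mean term, and neither section commits to adjusting for baseline drinking.
- Chance imbalance under valid randomization is not systematic bias. Correct: the shift in step 4 is conditional on an unlucky draw. Prespecified baseline adjustment would handle most of it without changing the randomization.
- If assignment really follows parent consent, teen answers are not yet available and stratifying on them is impossible. That is why the timing must be settled first.
- A reader might infer that the panel vendor makes the assignment. The sentence is passive, and the facilities section describes study software from the digital developer that also randomizes, so the holder of the list is not established.
- A reader might infer that about 91 drinkers determine the primary outcome. Weekly drinking and consequences are recalled over six months, and non-drinkers can start during follow-up, so the documents do not support this.

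**Conclusion.** The point holds as a low-cost design improvement, not as a fatal defect. The allocation method is unspecified beyond a random sequence, its timing is stated inconsistently, and nothing described balances baseline drinking. At the plan's national rates, a gap of 5 points or more in drinker share arises in about 23% of trials. At a 1.96-SE baseline imbalance, a change contrast could move by about 0.06-0.12 SD.

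These sizes rest on the national rates applying to this sample and on the assumed correlation of 0.4-0.7. The documents do not support the stronger conclusions that power is compromised by unequal arms, that the comparison is systematically biased, or that stratifying would eliminate the problem. It would not balance heavy drinkers or sexual-minority youth, both of whom can still fall unevenly.

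**What to change.** 1. Reconcile the Randomization paragraph with the two sections that place assignment after baseline, so that the arm is released when the teen baseline is submitted. State who holds the list.
2. Replace the random number table with a concealed, computer-generated permuted-block list with varying block sizes, stratified by baseline past-month alcohol use (yes/no) and teen birth sex: four strata. The bound in step 5 is for blocks of 4; larger blocks loosen it.
3. In the Aim 1 section, prespecify the two stratum factors, and preferably the baseline value of each primary outcome, as covariates in the comparison of follow-up outcomes.

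This needs no added participants or data collection, but it must be in place before enrolment. The cost is that two baseline answers must be passed to the assignment step. If that proves impracticable, item 3 alone deals with most of the risk to the estimate.

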beginning of PN. More specifically, parents will receive similar content, regardless of style, but the way that content is communicated will differ. For example, when presenting alternatives to drinking, content for partner style parents, it will be formatted around “how, what and why” questions they can use to engage their student in coming up with solutions together. Forceful parents will be given direct instruction guidance around consequences of risky drinking and directing them to alternative activities. A second example relates to framing content specific to the importance of having a collaborative, mutual conversation, which is not necessarily the natural orientation for forceful parents. Forceful parents receive this message: “Conversations will be most effective when your teens have the sense that they are collaborating with you and that you both have mutual interests.” whereas partner parents receive the following: “Communication is most effective when you both have a feeling of collaboration and mutual interest.”

**Design Features and Programming.** The PN curriculum will adhere to a VODEPS pedagogy – (V) visually engage the learner, (O) provide an overview of the level content, (D) define terms and learning objectives, (E) demonstrate and provide examples, (P) practice skills, and (S) summarize the level. PN is a mobile web app. A mobile web app functions similar to a native app on a smart phone or tablet computer. However, a mobile web app runs through the phone’s/computer’s web browser controlled by an external web server rather than running on the local device. There are several advantages to this approach: 1) Mobile web apps can be mobile device responsive to ensure cross-platform compatibility. 2) User experience is similar to a native mobile app, but content can be updated much more quickly than native apps that need to download/install a revised version. 3) Mobile web apps avoid the need to program for multiple operating systems (e.g., iOS or Android for smartphones/tablet computers), speeding development. 4) Use of mobile web app can be better tracked from the web servers than from a native app, leading to better evaluation of relationships between curriculum completion and substance abuse outcomes.

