**PN Program Analytics.**

Program analytics (i.e., log data) to be collected include

total time spent accessing PN, time spent on each module and activities within modules, and number of activities and modules completed. These data will be captured through HTML5 programming and downloaded into Excel. From this data, we will be able to examine the depth of parents’ immersion in the program and distinguish between users who quickly moved through the program versus those with a deeper level of engagement as well as assess accuracy and use them to assess effects of program exposure (i.e., dose).

**Fidelity of PN Use.** We will assess fidelity in several ways. First, we will use the program analytics described above to verify access to PN. Second, we will use practices to ensure that all parents carefully read the PN at least once. We will ask parents to rate each section of the PN in terms of how readable, useful, and interesting they were. Past studies on the Parent Handbook have shown that ratings tend to be uniformly positive, with means on 4-point scales ranging from 3.07 to 3.71 (SDs ranged from .55 to .94). Third, parents will be asked if they had discussed specific topics covered in the PN using 4-point scales ranging from (1) not at all to (4) a great deal. Past studies on the Parent Handbook have shown >70% of parents report they had discussed all topics. In our past studies, we have asked parents to underline segments of the Parent Handbook that resonate for them and make comments in the margins of the materials, and found that >70% return the materials with markings and comments throughout (almost all comments being uniformly positive). In the current study, we will have an option where parents can click on an icon to add a comment on any section of the PN modules. We will encourage them to do so, letting them know that it will help us understand content they particularly like or feel needs to be refined. Based on our previous work, we anticipate >70% of the parents will read the PN thoroughly, rate the content positively, and communicate the content with their teens.

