**Attrition analyses.** We will first examine if the attrition is random by forming a dummy variable that indicates completion or drop-out at each assessment. The dummy variable will be correlated with key variables in the study (e.g., Group, drinking outcomes). In the past, we have observed nonsignificant correlations suggesting that the attrition has been random and then used the most advanced multiple imputation techniques to impute missing data. We then analyze all cases with the imputed data. Although we have not observed differential attrition by condition, we recognize the potential. We will reduce this possibility by providing the controls with an online link to the intervention at the completion of the 6-month assessment. Thus, all conditions will be identical except for the timing of intervention. However, if we should observe non-trivial correlations (e.g.,  $> .2$ ) between the dummy variable reflecting completers vs. drop-outs, we will include the dummy coded variable as a covariate in subsequent analyses and attempt to interpret significant effects.

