**Measurement Error.** Where possible, we will adopt strategies that explicitly model measurement error (e.g., use multiple indicators in SEM). For single indicator models, measurement error can be modeled by fixing error variances of measures at a priori specified values that map onto the reliability of these measures suggested by previous research. If it is a multi-item measure, we can create multiple indicators using split-half methods. In cases where we cannot formally model measurement error influences, we will take care to recognize biasing effects of measurement error when interpreting the results of statistical analyses.

**Covariates.** In our modeling efforts, there may be confounds with some of our core explanatory variables. These confounds will be addressed by statistically controlling for them as covariates in our estimating equations. The choice of covariates is non-trivial, and one must be careful not to engage in atheoretical

partialling. Our approach will be to control if: (1) it is thought to be a source of spuriousness, and/or (2) it is correlated with the key variable(s) in the model but is thought to have an independent effect on the criterion. We will carefully consider the role of variables and explore models as is theoretically appropriate.

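### Parenting Now use logs, recorded after randomisation, are ordered in as covariates in every analysis, including the Aim 1 efficacy comparison

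*Combined protocol and SAP*

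**What the plan says.** The instruction is in Approach, Objective 2, Data Collection and Measurement: "program analytics will be examined to help ensure fidelity to the intervention, and to be included as covariates in all analyses".

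The same section defines the variables: "Program analytics (i.e., log data) to be collected include total time spent accessing PN", together with time per module and counts of activities and modules completed. It also gives them a separate purpose, a dose (exposure) analysis. Fidelity of PN Use adds a third: "we will use the program analytics described above to verify access to PN". Design Features and Programming likewise looks ahead to "leading to better evaluation of relationships between curriculum completion and substance abuse outcomes".

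For the other arm, Participant Recruitment and Procedures says "Parents in the control condition will receive a link to that server to access publicly available SAMHSA alcohol prevention materials for parents". No use variable is defined for control parents, and no coding is given for them.

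The Aim 1 text specifies a 2 x 3 (group by time) MANCOVA on the outcomes, with an intent-to-treat analysis of everyone randomised. It adds sex, sexual orientation and gender identity as covariates. It does not say that the program analytics are left out.

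**The concern.** Aim 1 is the efficacy test, and dissemination depends on it. The arms are comparable because parents were randomised. How much of PN a parent then uses is a consequence of assignment and is also the route by which PN is meant to work: under Aim 2 the plan's own theory runs from PN content to parental skills, to communication, to teen behaviour. Holding use constant takes that route out of the group effect, so an effective program could be reported as ineffective.

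Two other parts of the plan might seem to prevent this, but do not. The intent-to-treat sentence fixes who is analysed and is silent on covariates, so all 400 dyads can be included while the group term is still adjusted for uptake. The general Covariates paragraph warns against adjustment without theory, but it neither names the analytics nor overrides the specific instruction. Its second criterion, "it is correlated with the key variable(s) in the model but is thought to have an independent effect on the criterion", could even be read to admit them.

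**Working it through.** **Inputs from the plan.** 400 dyads randomised equally; 280 dyads expected at 6 months (Participant retention); effects of 5–10% of outcome variance with power above 0.80 (Statistical Design and Power); a fidelity benchmark of 80% (Indicators of Success).

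**Assumed, not in the plan.** Two-sided alpha 0.05; controls coded 0; within-person correlation ρ = 0.5 with equal variances; *f*, the share of the effect proportional to use; CV, the coefficient of variation of use within the PN arm.

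**1. The plan's own power.** 5% of variance gives d = 2·√(0.05/0.95) = 0.459. For a single two-group comparison, power is 0.996 at N = 400 and 0.969 at N = 280 (0.989 and 0.938 with 2 numerator df). The stated figure of above 0.80 is reproduced.

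**2. What the group term estimates.** Fit Y = a + b·Group + c·Use with Use = 0 in controls. Then b is the PN-arm regression line read at zero use, minus the control mean. The assignment effect is b + c·(mean PN use). Hence b = (1 − f)·d:

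| f | 0 | 0.25 | 0.5 | 0.75 | 1 |
|---|---|---|---|---|---|
| b (SD) | 0.46 | 0.34 | 0.23 | 0.11 | 0.00 |

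This does not depend on the scale of the use measure, and grand-mean centring does not change it.

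**3. Precision.** With PN use of mean m and SD s, the R² of group on use is (m²/4)/(s²/2 + m²/4). The variance inflation is therefore 1 + m²/(2s²) = 1 + 1/(2·CV²):
- CV 1.0: 1.5
- CV 0.5: 3.0
- CV 0.3: 6.6
- 0/1 use at 80%: 1 + 0.64/(2 × 0.16) = 3.0

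**4. Power for the change contrast** (mean of the two follow-ups minus baseline, with use given its own coefficient at each wave). The contrast SD is √((1+ρ)/2 + 1 − 2ρ) = 0.866. The noncentrality is (1 − f)·0.459/0.866·√(N/4)/√inflation. At N = 400, f = 0 and inflation 3.0 this is 5.30/1.73 = 3.06.

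| | Use left out | f = 0 | f = 0.5 | f = 1 |
|---|---|---|---|---|
| N = 400, inflation 3.0 | 1.00 | 0.86 | 0.33 | 0.05 |
| N = 280, inflation 3.0 | 0.99 | 0.72 | 0.25 | 0.05 |
| N = 400, inflation 1.5 to 6.6 | 1.00 | 0.99 to 0.54 | 0.58 to 0.18 | 0.05 |
| N = 280, inflation 1.5 to 6.6 | 0.99 | 0.95 to 0.41 | 0.44 to 0.14 | 0.05 |

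At f = 0 and inflation 3.0, varying ρ from 0.3 to 0.7 gives 0.73 to 0.98 (N = 400) and 0.58 to 0.91 (N = 280). For a single follow-up comparison without baseline, power falls from 0.996 to 0.75 and from 0.97 to 0.60.

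**5. Simulation check.** A three-wave model with 200 per arm, ρ = 0.6 and a true effect of −0.459 SD gave an adjusted group-by-time term of −0.46, −0.23 and 0.00 SD for f = 0, 0.5 and 1. Without the use covariate, power was about 1.00 throughout.

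**6. Selection into use.** Suppose there is no true effect, 80% of parents would use PN, and the teens of would-be users sit 0.3 SD lower at every wave. The zero-use PN group is then compared with a control mean of 0.8 × (−0.3) = −0.24. The adjusted follow-up comparison is off by +0.24 SD without baseline and by +0.12 SD with baseline (type I error about 0.12 at N = 400 and 0.10 at N = 280). The change model is off by 0.

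**The case against.** The strongest reply is that the damage depends on choices the plan leaves open, and zero coding is the worst of the workable ones.

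- **Centring use within the PN arm**, with controls at 0, keeps the group term at the assignment effect (−0.458 SD in simulation).
- **One common use coefficient across waves** leaves the group-by-time contrast unchanged in complete data.
- **Leaving controls missing** drops the whole control arm from a complete-case fit, an error nobody would overlook.
- **Logging control parents too** is possible: they use the same server, and Intervention Materials and Follow-Up Surveys promises identical fidelity questions and equal navigation time. Suppose the whole effect acts through PN use, control use has no effect, and there is no selection into use. The group term is then −0.46 SD if mean use is equal in the two arms, −0.40 if controls average 80% of PN use, −0.28 at 50% and about zero at none.

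It can also be said that the clause is one phrase in a measurement overview, and that the Aim 1 text names its own covariates without the analytics.

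These points are correct and set the limits of the finding: collapse to zero is one outcome among several. They do not rescue the plan. It specifies neither centring, nor control logs, nor a common coefficient, and a MANCOVA on three waves gives each covariate a coefficient per wave by default. The instruction covers all analyses, and the dose analysis is named separately, so the clause cannot be read as meaning only that. One qualification stands: when no part of the effect acts through use, the adjusted estimate is free of bias only if use is unrelated to prognosis, or in a change model where that relation is stable over time.

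**Conclusion.** The concern holds and should be fixed before analysis. A written rule puts post-randomisation treatment uptake into the primary efficacy model, and nothing in the plan removes it. With controls coded 0 and wave-specific use coefficients, the group term loses the share *f* of the effect that acts through use: from nothing at f = 0 to all 0.46 SD at f = 1. Precision is lost even at f = 0, where power at 280 dyads and inflation 3.0 is 0.72, below the plan's 0.80. The size rests on the assumed *f*, variation in use and within-person correlation, and on the coding and model form that the plan leaves open. The absence of any exemption for Aim 1 rests on none of these.

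**What to change.** Under Data Collection and Measurement, delete the closing clause that makes the analytics covariates. Under Aim 1, add a sentence saying that program-use data are not covariates in any comparison of the randomised arms; let it name the growth-trajectory analysis of efficacy described after Aim 2. Keep the analytics for the fidelity check and the dose analysis, and label the latter secondary and non-randomised.

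Do not widen the new sentence to baseline covariates only without also revisiting Attrition analyses. If drop-out shows non-trivial correlations, that section says "we will include the dummy coded variable as a covariate in subsequent analyses", and the indicator is itself post-randomisation.

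The cost is one deletion, one sentence and a label. The deletion also takes the analytics out of the Aim 2 models as routine covariates, where they could distort the group paths in the same way. The planned group-by-time model and the drop-out handling are unchanged, and no extra data or participants are needed.
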